**Table 10-1 Grouped Percentiles for stature-for-age Z-scores**

Calculated Percentiles (%)	Grouped Percentiles (%)
0 – <7.5	5
7.5 – <17.5	10
17.5 – <37.5	25
37.5 – <62.5	50
62.5 – <82.5	75
82.5 – <92.5	90

The sex and age-adjusted normal range for SBP and DBP for each grouped stature percentiles is based on the SBP/DBP table in the National Heart, Lung, and Blood Institute (NHLBI) website (<http://www.nhlbi.nih.gov/health-pro/guidelines/current/hypertension-pediatric-jnc-4/blood-pressure-tables>). The mean value at each time point will be plotted for SBP and DBP. Listings will be provided for the vital signs parameters. Listing of subjects with potentially abnormal SBP or DBP will also be provided.

### **10.5.5 Pulse Oximetry**

For the pulse oximetry measurements, a summary of raw values and change from parent study baseline will be provided at each scheduled time point in the Current Study Period for the percent of oxygen saturation based on the 116 Safety Set.

The number and percentage of subjects with shift changes from parent study baseline (normal/missing and low according to the reference range) to the lowest percent of oxygen saturation during the Treatment-emergent Period of the Current Study Period, will be summarized based on the 116 Safety Set.

Listings will be provided for the pulse oximetry measurements.

### **10.5.6 Ophthalmological Examinations**

OE findings will be presented as a data listing.

### **10.5.7 Spirometry**

Spirometry data will be summarized descriptively at each Study 116 visit based on the 116 Safety Set for subjects who are  $\geq 3$  years of age at screening in Study 115B based on 116 FAS. Spirometry measurements from subjects who turn 3 years of age during the Study 115B or Study 116 will not be included in the summary. The raw values and absolute change/relative change from parent study baseline will be summarized at each scheduled time point of the Current Study Period.

The following parameters: forced expiratory volume in 1 second (FEV1 (L)), percent predicted FEV1 (ppFEV1), forced vital capacity (FVC (L)), percent predicted FVC (ppFVC), FEV1/FVC and ppFEV1/FVC as well as forced expiratory flow (FEF25%-75% (L/s)) and percent predicted FEF (ppFEF25%-75%) will be summarized using descriptive statistics at each visit in the Current Study Period. The percent predicted values ppFEV1, ppFVC, ppFEV1/FVC and ppFEF25%-75% will be calculated using the standards of Global Lungs Initiative (GLI) as described in [Appendix G](#).

In addition, a listing containing individual subject data will be provided.

### **10.5.8 Physical Examination**

Physical Examination findings will be presented as a data listing only.

### **10.5.9 Other Safety Analysis**

Not Applicable

## **11 SUMMARY OF INTERIM AND IDMC ANALYSES**

### **11.1 Interim Analysis**

No interim analysis is planned.

### **11.2 IDMC Analysis**

Safety and tolerability data was reviewed by the IDMC to ensure the safety of the subjects in the study based on the data cut as of 09 March 2018. Procedural details of the IDMC's structure and function and data planned for review is outlined in the IDMC charter. The statistical analysis methodology was specified in the IDMC analysis plan. DMC charter and IDMC SAP were finalized before the IDMC review meeting.

### 13 LIST OF APPENDICES

#### Appendix A: Schedule of Assessments

**Table 13-1 Study VX16-809-116: Treatment Cohort - Treatment Period and Safety Follow-up Visit**

Event/Assessment a	Treatment Period					ETT Visit b	Safety Follow-up Visit c
	Day 1 d	Day 3 (± 1 Day)	Day 15 (± 3 Days)	Weeks 12, 24, 36, 48, 60, 72, 84 (± 7 Days)	Week 96 (± 7 Days)	As Soon as Possible After the Last Dose	2 Weeks (± 4 Days) After the Last Dose
Informed consent/assent	X						
Clinic visit	X		X	X	X	X	X
Telephone contact e		X					
Stature and weight f	X		X	X	X	X	X
Vital signs g	X h		X	X	X	X	X
Pulse oximetry g	X		X	X	X	X	X
OE s i	X			Week 48 j	X ik	X ik	X ik
Full PE l	X			Weeks 24, 48, 72	X	X	X
Abbreviated PE	X m						

a Assessments will be performed before LUM/IVA dosing unless noted otherwise.  
b If the ETT Visit occurs 10 days or later after the last dose of LUM/IVA, the Safety Follow-up Visit will not be required (Section 9.1.2.3 of the protocol). Subjects who prematurely discontinue LUM/IVA treatment for AEs should be followed until the AE is considered resolved.  
c The Safety Follow-up Visit is required for 1) subjects who complete their ETT Visit <10 days after the last dose of LUM/IVA (footnote b and Section 9.1.2.3 of the protocol); and 2) subjects who interrupt LUM/IVA treatment and complete their Week 96 Visit <10 days after the last dose of LUM/IVA; it is not required for subjects who continue onto commercially-available, physician-prescribed LUM/IVA within 2 weeks (± 4 days) of completing LUM/IVA treatment at the Week 96 or ETT Visit.  
d For subjects at sites activated by the time of their Study 115B Safety Follow-up Visit, their Study 116 Day 1 Visit will be on the same day as their Study 115B Safety Follow-up Visit, and any Study 116 Day 1 assessments that were specified to be performed at the Study 115B Safety Follow-up Visit do not need to be repeated. If the Study 116 Day 1 Visit does not coincide with the subject’s Study 115B Safety Follow-up Visit, the subject will complete all Study 116 Day 1 assessments (except the OE if it was performed within the last 3 months before the visit). See Section 9.1.1 of the protocol for details.  
e Telephone contacts will be made to assess the subject’s status, any AEs, medications, treatments, and procedures.  
f If subjects can stand unassisted and follow directions, stature should be measured as height; otherwise, stature will be measured as length. Stature and weight must be measured with shoes off and while wearing light clothing. BMI will be derived from this assessment. See Section 11.4.3 of the protocol for details.  
g The subject should rest for at least 5 minutes before having vital signs and pulse oximetry measured. See Section 11.6.4 of the protocol for details.  
h Vital signs will be measured predose and at 1 hour (± 15 minutes), 2 hours (± 15 minutes), and 4 hours (± 15 minutes) postdose on Day 1.  
i An OE will be conducted by a licensed ophthalmologist. Subjects with documentation of bilateral lens removal do not need the OE. See Section 11.6.6 of the protocol for details.  
j Subjects may complete the OE within ± 1 week of the scheduled visit.

- k An OE will be conducted at the Week 96 Visit (or the ETT Visit if the subject does not have a Week 96 Visit, unless the discontinuation is due to initiation of treatment with commercially-available LUM/IVA), or the Safety Follow-up Visit.
- l Symptom-directed PEs will occur at any time during the study if triggered by AEs or if deemed necessary by the investigator. See Section 11.6.4 of the protocol for details.
- m An abbreviated PE will be performed 4 hours ( $\pm$  30 minutes) postdose on Day 1. See Section 11.6.4 of the protocol for details

**Table 13-1 Study VX16-809-116: Treatment Cohort - Treatment Period and Safety Follow-up Visit**

Event/Assessment a	Treatment Period					ETT Visit b	Safety Follow-up Visit c
	Day 1 d	Day 3 (± 1 Day)	Day 15 (± 3 Days)	Weeks 12, 24, 36, 48, 60, 72, 84 (± 7 Days)	Week 96 (± 7 Days)	As Soon as Possible After the Last Dose	2 Weeks (± 4 Days) After the Last Dose
Standard 12-lead ECGs n	X		X	Week 48	X	X	X
Serum chemistry o	X		X	Weeks 12, 24, 36, 48, 72	X	X	X
Hematology o				Weeks 12, 24, 36, 48, 72	X	X	X
Coagulation studies o				Week 48	X		
Urinalysis o	X			Week 48	X		
Qualitative microbiology cultures p	X			Weeks 24, 48, 72	X	X	
Immunoreactive trypsinogen	X			Week 48	X		X
Fecal elastase-1 q	X			Week 48	X		X
Sweat chloride r	X			Weeks 24, 48	X		X
LCI (optional) s	X			Weeks 24, 48	X		X
Spirometry t	X u		X	Weeks 24, 48	X	X	X
Other events related to outcome v	X		X	X	X	X	X
LUM/IVA dosing w	LUM/IVA q12h						
Observation 4 hours after the first dose	X						
Study drug count	X		X	X	X	X	

n A standard 12-lead ECG will be performed. The subject will be instructed to rest in the supine position for at least 5 minutes, if possible, before having an ECG performed. The

ECG will be performed before any other procedures that may affect heart rate, such as blood draws. See Section 11.6.5 of the protocol for details.

o See Section 11.6.2 of the protocol for details.

p See Section 11.4.7 of the protocol for details.

q Samples will be collected at the study center during the study visit; however, samples may be collected by the subject up to 24 hours before the study visit (e.g., at home) and brought to the study visit (Section 11.4.5 of the protocol). The sample may be collected pre- or postdose.

r The sweat chloride test will be conducted at approximately the same time as predose blood collections. At each time point, 2 samples will be collected, 1 sample from each arm (left and right). See Section 11.4.1 of the protocol for details.

s The LCI assessment (only subjects who are ≥3 years of age at Study 115B screening who consent/assent to the optional LCI Substudy in Study 115B and Study 116) should be performed pre-bronchodilator. See Sections 11.1 and 11.4.2 of the protocol for details. The assessment will be performed in multiple replicates and before the spirometry assessment.

t Spirometry (only subjects who are ≥3 years of age at Study 115B screening) should be performed pre-bronchodilator. See Sections 11.1 and 11.6.7 of the protocol for details.

u Day 1 spirometry will be performed before LUM/IVA dosing and at 2 hours (± 30 minutes) and 4 hours (± 30 minutes) postdose.

- v Other events related to outcome include assessments relating to pulmonary exacerbations, administration of antibiotic therapy for sinopulmonary signs or symptoms, and hospitalizations (Section 11.4.4 of the protocol).
- w LUM/IVA will be administered q12h ( $\pm$  2 hours) within 30 minutes of consuming fat containing food (Section 9.6 of the protocol). On days of scheduled visits, the dose will be administered at the site after predose assessments have been completed. The last dose will be the dose administered before the Week 96 Visit. See Section 9.6 of the protocol for dose determination details.

**Table 13-1 Study VX16-809-116: Treatment Cohort - Treatment Period and Safety Follow-up Visit**

Event/Assessment a	Treatment Period					ETT Visit b	Safety Follow-up Visit c
	Day 1 d	Day 3 (± 1 Day)	Day 15 (± 3 Days)	Weeks 12, 24, 36, 48, 60, 72, 84 (± 7 Days)	Week 96 (± 7 Days)	As Soon as Possible After the Last Dose	2 Weeks (± 4 Days) After the Last Dose
Medications, treatments, and procedures review	Continuous from signing of ICF through Safety Follow-up Visit (if required)						
Adverse events	Continuous from signing of ICF through Safety Follow-up Visit (if required)						

AE: adverse event; BMI: body mass index; ECG: electrocardiogram; ETT: Early Termination of Treatment; ICF: informed consent form; IVA: ivacaftor; LCI: lung clearance index; LUM: lumacaftor; OE: ophthalmological examination; PE: physical examination; q12h: every 12 hours

**Table 13-2 Study VX16-809-116: Observational Cohort**

Event/Assessment	Day 1a	Long-term Follow-up Telephone Contact Weeks 48 and 96 (± 4 weeks)	Early Termination Telephone Contactb
Informed consent/assent	X		
Clinic visit	X		
Telephone contact		X	X
Serious adverse events	Continuous from signing of ICF through Week 96 or Early Termination Telephone Contact		

ICF: informed consent form; IVA: ivacaftor; LUM: lumacaftor

- a For subjects at sites activated by the time of their applicable Study 115B visit (i.e., the Week 24 Visit or the Safety Follow-up Visit, if required), their Study 116 Day 1 Visit will be the same day as their applicable Study 115B visit, and any Study 116 Day 1 assessments that were specified to be performed at the applicable Study 115B visit do not need to be repeated. If the Study 116 Day 1 Visit does not coincide with the subject’s applicable Study 115B visit, the subject will complete all Study 116 Day 1 assessments. See Section 9.1.1 of the protocol for details.
- b Subjects who become eligible to receive commercially-available, physician-prescribed LUM/IVA, and who choose to continue onto commercially-available LUM/IVA, must have an Early Termination Telephone Contact to terminate study participation

## **Appendix B: Standards for Safety and Efficacy Variable Display in TFLs**

### **Continuous Variables**

The precision for continuous variables has been specified in the Vertex Standard Programming Rules document (Version 1.0, December 2015):

**Categorical Variables**: Percentages will be presented to 1 decimal place.

## Appendix C: Analysis Visit Windows for Safety and Pharmacodynamic Assessments

**Table 13-3 Visit Window Mapping Rules for Safety Measurements (809-116)**

Assessments	Study 116 Visit	Target Study Day	Visit Window (in study days)

 
• Weight and stature
 
• Vital signs
 
• Pulse oximetry
 
	116 Day 15	15	(1, 50]
	116 Week 12	85	[51, 127]
	116 Week 24	169	[128, 211]
	116 Week 36	253	[212, 295]
	116 Week 48	337	[296, 379]
	116 Week 60	421	[380, 463]
	116 Week 72	505	[464, 547]
	116 Week 84	589	[548, 631]
	116 Week 96	673	[632, 680]
	116 Follow-up Visit	687	Nominal Visit

 
• Standard digital ECG
 
	116 Day 15	15	(1, 176]
	116 Week 48	337	[177, 505]
	116 Week 96	673	[506, 680]
	116 Follow-up Visit	687	Nominal Visit

 
• Labs                             
 
○ Chemistry
 
 
 
	116 Day 15	15	(1, 50]
	116 Week 12	85	[51, 127]
	116 Week 24	169	[128, 211]
	116 Week 36	253	[212, 295]
	116 Week 48	337	[296, 421]
	116 Week 72	505	[422, 589]
	116 Week 96	673	[590, 680]
	116 Follow-up Visit	687	Nominal Visit

 
• Labs                             
 
○ Hematology
 
 
 
	116 Week 12	85	(1, 127]
	116 Week 24	169	[128, 211]
	116 Week 36	253	[212, 295]
	116 Week 48	337	[296, 421]
	116 Week 72	505	[422, 589]
	116 Week 96	673	[590, 680]
	116 Follow-up Visit	687	Nominal Visit

 
• Labs                             
 
○ Coagulation
 
 
 
	116 Week 48	337	(1, 505]
	116 Week 96	673	[506, 680]
	116 Follow-up Visit	687	Nominal Visit

 
• Spirometry
 
	116 Day 15	15	(1, 92]
	116 Week 24	169	[93, 253]
	116 Week 48	337	[254, 505]
	116 Week 96	673	[506, 680]
	116 Follow-up Visit	687	Nominal Visit

 
• Sweat chloride
 
• LCI
 
	116 Week 24	169	(1, 253]
	116 Week 48	337	[254, 505]
	116 Week 96	673	[506, 680]
	116 Follow-up Visit	687	Nominal Visit

---

• FE-1			
• IRT	116 Week 48	337	(1, 505]
	116 Week 96	673	[506, 680]
	116 Follow-up Visit	687	Nominal Visit

---

The study days are based on the first dose in 116.

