### 9.1.2.3 Early Termination of Treatment

Subjects who prematurely discontinue LUM/IVA treatment will be asked to complete the ETT Visit as soon as possible after the last dose of LUM/IVA. The assessments to be completed are listed in Table 3-1. If the ETT Visit occurs 10 days or later following the last dose of LUM/IVA, then the ETT Visit will replace the Safety Follow-up Visit, (i.e., the assessments performed will be those specified for the ETT Visit), and a Safety Follow-up Visit will not be required.

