#### Treatment Cohort

**Continuous variables** will be summarized using descriptive summary statistics: number of subjects, mean, standard deviation (SD), standard error (SE), median, minimum value (Min), and maximum value (Max). Precisions of the summary for continuous variables are detailed in [Appendix B](#).

**Categorical variables** will be summarized using counts and percentages. Percentages will be presented to 1 decimal place.

**Baseline:** The baseline value is defined as the most recent non-missing measurement (scheduled or unscheduled) before intake of the first dose of study drug in Study 115B, except specified otherwise.

- For ECGs, the baseline will be defined as the average of the pretreatment measurements on the start of Study 115B.
- For LCI-related parameters, the values at each visit will be calculated from the technically acceptable replicates. The baseline of LCI will be the most recent non-

missing value calculated from the technically acceptable replicates before the initial administration of study drug in the Study 115B.

- For sweat chloride, the values at each visit will be based on the averaged measurements from left and right arms. The baseline is defined as the average of the values at screening and the pretreatment measurement on Day 1 of Study 115B. For assessments where there is only 1 pre-first dose sweat chloride measurement available, that measurement will be considered the baseline.

**Change (Absolute Change) from baseline** will be calculated as

$$\text{Post-baseline value} - \text{Baseline value.}$$

**Relative change from baseline** will be calculated and presented in percentage as

$$100 \times (\text{Post-baseline value} - \text{Baseline value}) / \text{Baseline value.}$$

**Unscheduled visits:** Unscheduled visit measurements will be included in the analysis as follows:

- In scheduled visit windows per specified visit windowing rules.
- In the derivation of baseline measurements.
- In individual subject data listings as appropriate.

**Visit windowing rules:** [Appendix C](#) defines the visit window mapping rules to derive the analysis visits for study 116.

Repeated observations within the same visits window:

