- For all PD parameters, if there are multiple measurements within a visit window, the record at the scheduled visit will be used. If there are no measurements at the scheduled visit, then 1) the record closest to the target day will be used; or 2) if there are multiple records with the same distance to the target day, the latest record will be used.
- For all safety parameters, if there are multiple measurements within a visit window, then 1) the record closest to the target day will be used; or 2) if there are multiple records with the same distance to the target day, the latest record will be used.

BMI, weight, and stature will follow visit window rules for PD parameters when being considered as PD endpoints; they will follow visit window rules for safety parameters when being considered as safety endpoints. Their corresponding z-scores will be assigned to analysis visits same as BMI, weight, and stature, respectively. Spirometry will follow the PD parameter window rule.

**Incomplete/missing data** will not be imputed, unless specified otherwise.

**Outliers:** No formal statistical analyses will be performed to detect or remedy the presence of statistical outliers, unless specified otherwise.

**Multiplicity:** No multiplicity adjustment will be performed and there is no hypothesis testing.

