### **Treatment Cohort**

Evaluating safety of long-term LUM/IVA treatment in the Treatment Cohort is the primary objective of this study. The overall safety profile of study drug will be assessed in terms of the following safety and tolerability endpoints:

- Treatment-emergent adverse events (TEAEs)
- Clinical laboratory values (serum chemistry, hematology, coagulation studies and urinalysis)
- ECGs (standard 12-lead)
- Vital signs
- Pulse oximetry
- OEs
- Spirometry (subjects  $\geq 3$  years age at screening in Study 115B)

The safety analysis will be performed based on the 116 Safety Set for the Current Study Period. Only descriptive summary statistics of safety data will be provided (i.e., no statistical hypothesis testing will be performed). All listings will be provided based on the 116 All Subjects Set.

The safety summaries described in the sections below will be performed for the Treatment Cohort based on the Current Study Period only.

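### Followed as written, the SAP's visit windows label early-termination ECG and spirometry records from day 506 onward as Week 96

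*SAP*

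**What the plan says.** SAP 10.1 states that Appendix C "defines the visit window mapping rules to derive the analysis visits for study 116". Table 13-3 there sets windows in study days and gives the origin: "The study days are based on the first dose in 116". The date of last dose plays no part. The Follow-up row, marked "Nominal Visit", is the only visit row assigned by name; a note below the table does the same for the Day 1 post-dose vital signs and spirometry. ETT does not appear. Unscheduled measurements are also placed "In scheduled visit windows per specified visit windowing rules".

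For ECG and spirometry the Week 96 window is days 506 to 680, with target day 673. The schedule of assessments (protocol Table 3-1, SAP Appendix A) has both collected at the ETT Visit and schedules neither between Weeks 48 and 96.

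Protocol 9.1.2.3 asks for the ETT Visit as soon as possible after the last dose and sets no upper limit. If it falls 10 or more days after that dose, "then the ETT Visit will replace the Safety Follow-up Visit".

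The by-visit laboratory, ECG and vital-sign summaries (SAP 10.5.2 to 10.5.4) take in all Study 116 measurements. The spirometry summary (SAP 10.5.7) has no on-treatment restriction.

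**The concern.** A Week 96 row in a long-term safety table will be read as the children's status after 96 weeks of treatment. Under these rules it can also hold a value from a child who stopped soon after Week 72, possibly measured some days off drug. Two children measured at a similar time after their last dose can be labelled differently: one as Follow-up, because the visit was recorded under that name, the other as Week 96, because it was recorded as ETT.

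The SAP says: "Evaluating safety of long-term LUM/IVA treatment in the Treatment Cohort is the primary objective of this study". Week 96 is the longest treatment time point, so its label should mean what it says. If a drug effect reverses after stopping, ETT values in this row also pull the mean change toward zero.

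**Working it through.** **1. Reproduce the window.** Target day = 7 × week + 1, so Week 48 is day 337, Week 72 is 505, Week 96 is 673 and Follow-up is 687. Each edge is the midpoint between neighbouring target days, rounded down.

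- Lower edge for ECG and spirometry: (337 + 673)/2 = 505, so Week 96 opens on day 506.
- Upper edge: (673 + 687)/2 = 680.

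The same rule reproduces every edge in Table 13-3.

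**2. How early a Week 96 record may be.**

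| Assessment | Week 96 window | Days before target |
|---|---|---|
| ECG, spirometry | 506–680 | 673 − 506 = 167 (23.9 weeks) |
| Chemistry, hematology | 590–680 | 673 − 590 = 83 |
| Vital signs, weight and stature, oximetry | 632–680 | 673 − 632 = 41 |

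The late side is 680 − 673 = 7 days throughout. If an ETT Visit on day 506 came 10 days after the last dose, that dose was on day 496, which is 177 days (25.3 weeks) before target. Coagulation, sweat chloride, LCI, FE-1 and IRT share the 506–680 window but are not collected at ETT.

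**3. Do the tie-breaks prevent it?** For safety parameters, "if there are multiple measurements within a visit window, then 1) the record closest to the target day will be used". For PD parameters, whose rule spirometry follows, the scheduled-visit record is preferred, and "If there are no measurements at the scheduled visit, then 1) the record closest to the target day will be used". Both rules choose among records inside one window. A child who stops after day 505 normally has no other ECG or spirometry record there, and a Safety Follow-up record is kept out by its nominal assignment. The ETT record is therefore used.

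**4. Size, under a stated assumption.** The documents give no dropout rate for Study 116. Suppose the 10% stated for the 24-week Study 115B recurs every 24 weeks (168 days) at a constant hazard, from the 50 children expected. Suppose also that ETT falls on the day of stopping and every completer has a Week 96 record. The number still on treatment at day t is S(t) = 50 × 0.90^(t/168).

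- S(505) = 36.4 and S(672) = 32.8, so 3.6 children stop in days 506–672.
- ECG: 3.6 / 36.4 = 9.9% of Week 96 records are ETT records.
- Chemistry and hematology: S(589) − S(672) = 34.6 − 32.8 = 1.8, or 5.1%.
- Vital signs: S(631) − S(672) = 33.7 − 32.8 = 0.9, or 2.5%.

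For another 24-week dropout d, the ECG share is 1 − (1 − d)^(167/168): 5.0% at d = 5%, 14.9% at 15% and 19.9% at 20%.

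The spirometry count is lower. Testing is limited to children aged 3 or more at Study 115B screening, and protocol 9.3.3 expects reproducible results in only a minority.

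**5. Bound on dilution.** Let a share p of Week 96 records be ETT records, let a fraction f of those have fully lost an effect Δ, and let the rest keep it. The Week 96 mean is then (1 − pf)Δ. Since f is at most 1, the dilution is at most p.

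**The case against.** The strongest reply is that a reader might infer too much. Four stronger readings are tempting, and the documents do not support them.

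- **That every ETT value is off drug.** ETT is requested promptly after the last dose, and 10 or more days is the fallback case. The documents also expect some children to stop because they move to commercial LUM/IVA (protocol 9.1.2.2, SAP 10.2.1), and these may still be taking it. What remains is that the treatment-duration label is wrong for an early stopper in the trial, whatever the drug status on the day.
- **That the safety conclusions are compromised.** TEAE tables, threshold counts, and the ECG and oximetry shift tables use the Treatment-emergent Period and not these windows. The analysis is descriptive with no hypothesis testing, so neither error rates nor power are touched.
- **That this is last-value imputation.** It is not. SAP 10.1 does not impute missing data, and the ETT value is a real measurement inside a window. Taking in data after discontinuation is also partly deliberate, given the all-measurements wording. That explains why the record is used, but not why a day-506 value should be called Week 96.
- **That many late Week 96 visits are lost.** Day 680 is exactly the protocol limit (673 + 7). Later visits stay in the listings and can still count in tables based on the Treatment-emergent Period. Nothing in the documents shows how visit dates scatter.

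It is also fair to say that the SAP never states how ETT is mapped. Because the protocol has a late ETT Visit replace the Safety Follow-up Visit, a programmer could assign it to the Follow-up row. But Table 13-3 does not say so, and read literally it points the other way.

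**Conclusion.** The point holds as a labelling fault in the by-visit summaries, mainly for ECG and spirometry and less for laboratory tests and vital signs. The table as written gives a Week 96 label to ETT records taken up to 167 days before target. It also gives a treatment-visit label to late ETT records that the protocol treats as replacing follow-up.

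How many children are affected is unknown. The figure of about 3.6 ECG records, or 10% of the Week 96 row, rests on carrying Study 115B's 10% dropout into each 24-week block; the range is 5% to 20% for dropout of 5% to 20%. That share is a ceiling on any dilution of the Week 96 mean. It is worth correcting before database lock because the remedy is cheap and Week 96 is the time point readers will look at first.

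**What to change.** In SAP Appendix C:

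1. Map an ETT record taken 10 or more days after the last dose to the 116 Follow-up Visit, in line with protocol 9.1.2.3. Flag or separate children who have already started commercial LUM/IVA, so that they are not read as off drug.
2. Show ETT records taken sooner than that in a separate ETT row instead of in the Week 96 row.
3. As a minor tidy-up, keep a nominal Week 96 visit after day 680 in the Week 96 row. Follow-up is assigned by name, so nothing collides.

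The cost is a few lines of SAP text and windowing code, plus a slightly smaller n at Week 96 for ECG and spirometry. No new data are needed.
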